#### **Analysis of Aim 1:**

Trial feasibility and adherence will be assessed using data from how often participants in the intervention group complete their IEO activities. This would be reported as the proportion of completed activities out of the total required per protocol. Similar analysis would be done for the control group and adherence to protocol too would be ascertained as a proportion of instance of protocol deviation out of total required activity per protocol. Participant satisfaction will be measured using an internally developed survey. Continuous and dichotomous data will be reported and assessed in a similar fashion as above.

#### **Analysis of Aim 2:**

Given the continuous nature of the scales used to assess stress, burnout and measures of well-being, differences between groups will be assessed with a parametric or non-parametric t-test. Although we expect that randomization should account for any differences between baseline characteristics, unadjusted and adjusted linear regression may be utilized in order to account for differences that persist. Our primary analyses will be assessed using intention-to-treat principles. In order to assess whether there are differences between baseline and at six weeks, we will employ the use of paired t-tests as appropriate.

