### B3. DESCRIPTION OF RESEARCH PROTOCOL

#### A. Study Design – Overview, Methods, Procedures

##### Study Overview:

This study involves evaluation of the effects of Inner Engineering Online (IEO) intervention by employing validated questionnaires aiming to measure stress and well-being in the form of a survey to company employees participating in the study.

In order to evaluate this, we randomize the participants into either of the two groups: one who participate in the IEO activities daily for the first 30 days and the other who do not participate in the IEO activities during the first 30 days. We then evaluate stress and burnout along with measures of well-being in these participants using validated electronic instruments at baseline and at the end of the 30 days. This is phase 1 of the study.

For the phase 2, we cross-over the group 2 participants and provide them with the IEO intervention. We follow them through another 30 days and then evaluate measures of stress, burnout and well-being using validated instruments at the end of these 30 days.

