### **Randomization:**

Participants will be randomized into one of the two groups using [Simple Randomization Technique] by REDCap. Participants will be randomized into:

1. Intervention Group: Participants will receive the Inner Engineering Online Intervention for a total of 30 days (4 weeks)
2. Control Group: Participants will read a book/journal of their choice for 25 minutes each day for a total of 30 days (4 weeks)

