### **Study Procedure:**

We will be administering a brief survey to willing participants after they provide electronic consent. If a participant decides to participate, they will receive a paper survey to complete, or they can complete the survey online via an anonymous REDCap survey link.

The Isha Foundation (which is responsible for the Inner Engineering Online Course) has agreed to send participants an email which contains detailed instructions on how to perform the IEO intervention after the electronic consent has been signed. The Isha Foundation receives the participating employee emails from the company, as they are the primary instructors for the intervention.

Subjects will be randomized following the consent into two groups.

**Group 1** will be asked to complete the Inner Engineering Online course which includes completing 7 meditation and yoga course modules in a duration of 30 days. They will be given an IEO activity diary and will be asked to keep a track of their progress. The activity diary will be collected from them on a

weekly basis for 30 days.

After 4 weeks (i.e., 30 days) they will be administered the same set of survey questionnaires which was asked before the intervention was administered. All communications will be conducted electronically or via phone.

**Group 2** will be asked to read a book or journal of their choice for 30 minutes at a time for 30 days. They will also be asked to complete a reading log every day to keep a track of their progress every day for 30 days.

Once 30 days is over they will be asked to complete the IEO intervention, which includes practice of meditation and yoga daily for another 30 days while maintaining an IEO activity diary. Group 2 will be asked to complete set of questionnaire at baseline, 30 days and after 60 days.

Surveys will be administered at two time points for group 1 at baseline and at 30 days, whereas three time points for group 2 that is baseline, 30 days and 60 days.

Apart from the surveys, the participants are advised to maintain a reading log or an activity diary for each week. These documents will be collected electronically, either via direct online submission or a scanned copy to be uploaded and sent to a redcap survey link at the end of each week. In order to account for national holidays and personal circumstances, participants may submit their activity diaries and/or reading logs within 2 weeks of the 30 day and 60 day time point.

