## B. Statistical Considerations

### a. *Sample Size Justification:*

In this survey based, randomized cross-over study, we are looking at the feasibility of implementing an Inner Engineering Online Intervention on a group of willing company employees. Since it is a feasibility study, we plan to enroll a minimum of 60 participants. Data from these participants will be used to power a larger trial based on the outcomes such as stress, burnout & overall well-being measured during the course of the study.

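### Aim 2 does not name the variable compared between arms and leaves baseline adjustment optional; a pre-specified ANCOVA on the baseline scores already collected would, at most plausible correlations, narrow the intervals

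*Combined protocol and SAP*

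**What the plan says.** The between-arm analysis of stress, burnout and well-being is defined only under B3.B.b, Analysis of Aim 2: "differences between groups will be assessed with a parametric or non-parametric t-test". The general Data Analysis text adds a Shapiro-Wilk check to choose between the parametric and non-parametric form, and a two-sided 0.05 level. Neither place says whether the day-30 score or the change from baseline is tested.

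On adjustment, the same paragraph says that "unadjusted and adjusted linear regression may be utilized in order to account for differences that persist". No covariate is named.

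The baseline scores are available. The Study Overview has both groups assessed "using validated electronic instruments at baseline and at the end of the 30 days". Under Study Procedure, group 1 at day 30 is covered by "they will be administered the same set of survey questionnaires which was asked before the intervention was administered", and for the controls "Group 2 will be asked to complete set of questionnaire at baseline, 30 days and after 60 days".

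The sample size is justified on feasibility: "we plan to enroll a minimum of 60 participants". The same section says the data will be used to power a larger trial.

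**The concern.** There are two gaps. First, the compared variable is not named. Two analysts who both follow the plan could test different quantities and report different estimates and intervals from the same surveys. With optional regression on unnamed covariates added, at least three analyses per scale are permissible, over several scales.

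Second, adjustment is tied to baseline differences that persist after randomization. Its main value in a randomized trial is different: removing the part of the outcome variance that the baseline score predicts, whether or not the arms happen to be balanced. An optional step triggered by imbalance does not reliably deliver that.

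At stake is the precision and reproducibility of the between-arm estimates. Validity is not in question.

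**Working it through.** **Inputs from the documents.** Minimum total 60 (Sample Size Justification); two arms by simple randomization (Randomization); two-sided 0.05 (Data Analysis); each scale at baseline and day 30 in both arms (Study Overview, Study Procedure).

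**Assumptions not in the documents.** A 30/30 split, no dropout, equal SD at both times, and a baseline-to-day-30 correlation ρ of 0.3, 0.5 or 0.7. The plan states no SD, effect size, correlation, power or dropout rate, and 60 has no stated derivation, so there is no plan figure to reproduce.

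**Formulas (95% CI half-width in SD units, N = 60).**
- Day-30 t-test: t(58) × √(2/30) = 0.517 at any ρ.
- Change-score t-test: t(58) × √(2/30 × 2(1 − ρ)).
- ANCOVA: t(57) × √(2/30 × (1 − ρ²) × (1 + 1/(N − 4))). The last factor, 1 + 1/56 = 1.0179, is the cost of estimating the slope.

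| | ρ = 0.3 | ρ = 0.5 | ρ = 0.7 |
|---|---|---|---|
| Day-30 t-test | 0.517 | 0.517 | 0.517 |
| Change-score t-test | 0.612 | 0.517 | 0.400 |
| ANCOVA | 0.498 | 0.452 | 0.373 |
| Variance ratio, ANCOVA / day-30 | 0.926 | 0.763 | 0.519 |
| Variance ratio, ANCOVA / change | 0.662 | 0.763 | 0.865 |
| N for a day-30 t-test to match 60 under ANCOVA | 65 | 79 | 116 |
| N for a change-score t-test to match | 91 | 79 | 69 |

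The matching N is 60 divided by the variance ratio; for example 60/0.763 = 78.6.

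**Effect of not naming the variable.** The change-score interval is √(2(1 − ρ)) times the day-30 interval: √1.4 = 1.18 at ρ = 0.3 (18% wider) and √0.6 = 0.77 at ρ = 0.7 (23% narrower). Which unadjusted test looks better therefore depends on the data. ANCOVA is narrower than both at each of these correlations.

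**Where ANCOVA stops gaining.** Against the day-30 test, the variances are equal when (1 − ρ²) × 1.0179 = 1, so ρ = √(1 − 1/1.0179) = 0.13. The worst case is ρ = 0, a variance ratio of 1.018. Against the change score, they are equal at ρ = 2/1.0179 − 1, about 0.96. The gain is small over the day-30 test at ρ = 0.3 (variance −7%) and over the change score at ρ = 0.8 (variance −8%).

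**Sensitivity (ρ = 0.3 / 0.5 / 0.7).**
- If 20% of day-30 surveys are missing (24 per arm): ANCOVA 0.56 / 0.51 / 0.42; day-30 0.58; change 0.69 / 0.58 / 0.45.
- The protocol says "Participants will be randomized into one of the two groups using [Simple Randomization Technique] by REDCap", so 30/30 is not guaranteed. At 22/38, the edge of the 95% binomial range for 60: ANCOVA 0.52 / 0.47 / 0.39; day-30 0.54; change 0.63 / 0.54 / 0.41.

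**Simulation check.** With bivariate normal data and 60,000 trials per case at 30 per arm, the variance ratios were 0.928, 0.763 and 0.518 against the day-30 test and 0.664, 0.766 and 0.863 against change. Each single test rejected a true null 4.9% to 5.1% of the time.

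**Separate inconsistency in the same paragraph.** The within-group tests are for "differences between baseline and at six weeks, we will employ the use of paired t-tests". Study Procedure and 30 day Follow Up schedule surveys at baseline, 30, 60 and 90 days, and none at six weeks. This has no bearing on the precision figures.

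**The case against.** The strongest reply is that adjusted regression is already in the plan, the t-test is valid, and a feasibility study has no powered efficacy endpoint to protect. On that view this is a refinement. Most of it is fair: there is no bias, no type I error problem and no lost promised power. But permission to adjust is not pre-specification, and no covariate is named.

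The natural reading may also be that the day-30 score is compared, since change from baseline has its own paired test. On that reading the change-score comparison falls away and the gain is the day-30 column alone: modest at ρ = 0.3, larger above. The text does not say so, however, and the ambiguity is cheap to remove.

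Three limits stand:
- The size of the gain depends on a correlation that the documents do not give. The extremes of 116 and 91 equivalent participants arise at opposite ends of the assumed range and against different comparators, so they cannot both apply to one scale.
- Rank tests were not compared; if the scores are skewed and the rank test is used, the gain is unquantified.
- The plan mentions p-values and no confidence intervals, so interval width here measures precision rather than a promised output.

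ANCOVA also needs each person's two surveys linked, and Study Procedure calls the survey link anonymous. B8 Data Security gives each subject a study ID with a crosswalk, and the planned paired tests already need the same linkage, so this is not an extra requirement.

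**Conclusion.** The concern holds. The Aim 2 between-arm comparison leaves its variable unnamed and its adjustment optional, although the covariate that would sharpen it is collected in both arms. With 30 per arm, equal SDs and correlations of 0.3 to 0.7, pre-specified ANCOVA narrows the 95% interval by 3.7% to 27.9% relative to a day-30 t-test, and by 18.6% down to 7.0% relative to a change-score t-test. The most it can lose at N = 60 is 1.8% in variance against the day-30 test, at zero correlation. The percentages rest on normal theory and assumed correlations; the missing specification does not. This is an improvement at no data cost to an otherwise valid analysis. It is worth making because Aim 2 sets out to quantify the effect and the results are meant to inform a larger trial.

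**What to change.** In Analysis of Aim 2, state for each scale that the primary between-group analysis is a linear regression of the day-30 score on randomized arm and that scale's baseline score, fitted regardless of observed baseline imbalance and reported as an adjusted difference with a 95% CI. Keep the t-test or rank test as a sensitivity analysis and name the variable it compares. State how participants with a missing baseline or day-30 survey are handled, and confirm that surveys are linked by study ID. In the same edit, reconcile the six-week reference, which also appears under Analysis of Aim 3, with the survey schedule.

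The cost is a few sentences and a standard SAS regression. No additional data or participants are needed.

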### B1. PURPOSE OF PROTOCOL

The purpose of this study is to determine the effects of a web based intervention called “Inner Engineering Online (IEO)” on the burnout states, stress and overall well-being of employees in a company.

The specific aims include:

1. To test feasibility and acceptance of IEO through assessment of participation, compliance, protocol adherence & study satisfaction.
2. To quantitatively assess the effects of IEO on measures of Burnout, Stress & well-being among the participating employees.
3. To determine the effect of IEO on measures of well-being among control employees after they cross over to the intervention group at the end of first phase.

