### b. *Data Analysis:*

Baseline characteristics of participants will be recorded. Continuous data will be presented as means  $\pm$  standard deviation or median (interquartile range) depending on the distribution of the data and assessed with a parametric or non-parametric t-test, as appropriate. Normality will be assessed with the Shapiro-Wilk test. Categorical data will be presented as frequencies and proportions and assessed with a chi-square or Fisher's exact test. SAS 9.4 (SAS Institute Inc., Cary, NC) will be used for all analyses with two-sided p-values  $< 0.05$  considered statistically significant.

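### Aim 2 is to quantify the effect of IEO, but the planned result is a significance test; no between-arm difference with a confidence interval is specified

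*Combined protocol and SAP*

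**What the plan says.** Section B1 gives Aim 2 as "To quantitatively assess the effects of IEO on measures of Burnout, Stress & well-being among the participating employees", and section B2 repeats it in similar terms.

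The Sample Size Justification (B3.B.a) rests on feasibility alone: "Since it is a feasibility study, we plan to enroll a minimum of 60 participants". It gives no effect size, SD, power or precision target. It adds that "Data from these participants will be used to power a larger trial", with stress, burnout and well-being as the outcomes concerned.

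The Data Analysis section (B3.B.b) describes continuous data by mean and SD, or by median and IQR, according to distribution. Its decision rule is "two-sided p-values $< 0.05$ considered statistically significant".

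The Analysis of Aim 2 then states that "differences between groups will be assessed with a parametric or non-parametric t-test". It adds that "unadjusted and adjusted linear regression may be utilized in order to account for differences that persist". Within-group change is to be examined by paired t-tests. The documents nowhere mention a confidence interval, and nowhere name the between-arm difference as a quantity to be reported.

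**The concern.** An aim to quantify an effect is met by an estimate and its uncertainty. The specified output is a test result, in a study whose size was not chosen to make that test decisive. At about 30 per arm, quite different true effects can lead to the same verdict on a given score.

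Two uses of the results depend on the missing quantity. The larger trial needs to know which differences remain plausible, and a p-value does not show that. Aggregate results also go to the company and to the course provider (section B10), and both could take a non-significant score as evidence of no effect if no interval stands beside it.

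**Working it through.** **The plan's own figure.** The minimum of 60 cannot be reproduced, because no effect size, SD, power or precision is given. For orientation, 80% power for a 0.5 SD difference at two-sided 0.05 needs 2 × (1.960 + 0.842)² / 0.5² = 62.8, so 63 per arm by the normal approximation. It is 64 per arm, or 128 in total, with the t distribution.

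**Inputs from the documents**
- Total of at least 60 (B3.B.a).
- Two groups by simple randomization, no ratio stated (B3.A, Randomization).
- Two-sided 0.05 (B3.B.b).
- Randomized comparison at baseline and day 30 (B3.A, Study Overview).

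**Assumptions, none of them in the documents**
- Equal allocation, so 30 per arm.
- True effects of 0.3, 0.4 and 0.5 SD.
- Loss of 0%, 20% or 30%, giving 30, 24 or 21 analysed per arm.

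**Power per score, unadjusted t-test.** The noncentrality parameter is d / √(2/n), compared with t(0.975, 2n−2). For n = 30 and d = 0.5 this is 0.5 / 0.2582 = 1.94 against a critical value of 2.002, which gives 48%.

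**Half-width of the 95% CI, in SD units.** The formula is t(0.975, 2n−2) × √(2/n). For n = 30: 2.002 × 0.2582 = 0.517. For n = 24: 2.013 × 0.2887 = 0.581.

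| Analysed per arm | Power at 0.3 SD | Power at 0.4 SD | Power at 0.5 SD | CI half-width |
|---|---|---|---|---|
| 30 | 21% | 33% | 48% | 0.52 SD |
| 24 | 17% | 27% | 40% | 0.58 SD |
| 21 | 16% | 24% | 35% | 0.62 SD |

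Averaging over the unequal arms that simple randomization of 60 can produce changes the 0.5 SD figure only from 48% to 47%. The effect detectable with 80% power at 30 per arm is 0.74 SD.

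**What the verdict hides.** Take two possible observed results on one score at 30 per arm:
- Observed 0 SD: 0 ± 0.52, so −0.52 to 0.52.
- Observed 0.4 SD: 0.4 ± 0.52, so −0.12 to 0.92.

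Both are non-significant. The first excludes a 0.8 SD benefit and the second does not. The interval separates them; the verdict does not.

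**Effect of baseline adjustment.** Multiply the half-width by √(1 − r²), where r is the assumed correlation between the baseline and day-30 scores. At 30 per arm this gives about 0.45 SD for r = 0.5 and 0.37 SD for r = 0.7. Power at 0.5 SD rises to about 59% and 76%.

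**Does other text already supply the estimate?**
- Summaries by mean, SD and n let a reader derive the difference and its interval, although the plan does not say that it will.
- Medians and IQRs do not reliably allow this, and a rank test gives no effect estimate unless one is requested.
- A regression coefficient would be an estimate, but the regression is optional and tied to baseline imbalance, and no coefficient or interval is named as output.
- The paired tests address change within a group, not the difference between groups.

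**The case against.** The strongest reply is that the plan already contains more than tests. It provides for descriptive summaries, and it allows unadjusted and adjusted regression. Where means, SDs and group sizes are published, anyone can compute the difference and its interval, and the SDs are what a later sample-size calculation needs. The study calls itself a feasibility study, and nothing in it says that a non-significant result will be read as no effect. These points stand, and they rule out several stronger readings that a reader might infer:

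- *That the plan yields nothing except tests, or leaves Aim 2 without any usable answer.* The planned summaries and optional regression contradict this. The gap is that the estimate and interval are not assured, most clearly when the median and rank-test route is taken.
- *That a moderate effect would usually be missed.* At an assumed 0.5 SD with all 60 analysed, power is 48%, close to a coin toss. It falls to 35–40% only with an assumed 20–30% loss. It passes 50% with 64 analysed in total, or with baseline adjustment at r of about 0.3 (52%), and 60 is a minimum.
- *That a non-significant result is compatible with anything from no effect to a large one.* An observed zero gives −0.52 to 0.52 SD, which excludes a large effect.
- *That Aim 2 as a whole would probably come out non-significant.* The questionnaires yield eight scores, counting three burnout dimensions. In a simulation of eight t-tests at 30 per arm with a true 0.5 SD effect on every score, at least one was significant in 88%, 79% and 65% of trials for inter-score correlations of 0.5, 0.7 and 0.9. At 0.4 SD the figures were 76%, 65% and 52%. A mixed picture is more likely than a uniformly negative one.
- *That the same fault can be sized for Aim 1.* Adherence there is completed activities over required activities. No per-participant threshold is defined, so an interval for a proportion of adherent participants has no basis in the plan.

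What the reply does not answer is the absence of a specified between-arm estimate with its uncertainty.

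**Conclusion.** The point holds as a gap in the specified Aim 2 output. The aim calls for an effect size; the plan specifies a test at p<0.05 and does not commit to a between-arm difference or an interval. That conclusion comes from the text and needs no assumed effect.

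The size of the consequence does rest on assumptions: equal arms, an unadjusted t-test, and standardized effects and losses that the documents do not give. On those, a single score has about 33% power at 0.4 SD and 48% at 0.5 SD with 30 per arm, and 27% and 40% with 24 per arm. The interval half-width is 0.52 or 0.58 SD. A significance verdict on any one score is therefore a weak guide to how large the effect is.

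This is a matter of analysis and reporting. It does not show that 60 is the wrong number for a feasibility study.

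**What to change.** In the Analysis of Aim 2, state that:

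1. The main result for each score is the IEO-minus-reading difference at day 30 with its 95% CI, preferably from a regression adjusted for the baseline value of that score. The baseline values are already collected.
2. If the non-parametric branch is used, the Hodges-Lehmann estimate of the shift is reported with its 95% CI.
3. P-values are secondary, and p≥0.05 is not read as absence of effect.
4. Aim 2 gives preliminary estimates from a study not sized to test them.

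This costs a few sentences, with no new data and no change in sample size. The small downside is that the wide intervals become visible. Baseline adjustment would narrow them to the extent that baseline and day-30 scores are correlated.

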#### **Analysis of Aim 3:**

To assess the effect of IEO intervention on the control group following its cross-over to the intervention will be assessed using a parametric or non-parametric t-test. Although we expect that randomization should account for any differences between baseline characteristics, unadjusted and adjusted linear regression may be utilized in order to account for differences that persist. Our primary analyses will be assessed using intention-to-treat principles. In order to assess whether there are differences between baseline and at six weeks, we will employ the use of paired t-tests as appropriate.

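### Intention-to-treat is claimed for Aims 2 and 3, but the stated method is an unadjusted t-test with no missing-survey rule, so it uses only people with a follow-up score and is biased if missingness relates to outcome differently by arm

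*Combined protocol and SAP*

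**What the plan says.** All references are to the combined protocol and SAP, section B3.

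- **Analysis of Aim 2.** For the stress, burnout and well-being scales, "differences between groups will be assessed with a parametric or non-parametric t-test". The section does not say whether the test is on day-30 scores or on change from baseline.
- **Adjustment.** In the same section, "unadjusted and adjusted linear regression may be utilized in order to account for differences that persist". This is permission, not commitment; no covariates are named, and the baseline score is not among any listed.
- **Within-group change.** "we will employ the use of paired t-tests as appropriate".
- **Principle.** "Our primary analyses will be assessed using intention-to-treat principles". The sentence recurs under Analysis of Aim 3, where the effect in controls "following its cross-over to the intervention will be assessed using a parametric or non-parametric t-test".
- **Sample Size Justification.** "Since it is a feasibility study, we plan to enroll a minimum of 60 participants". The data are then to be used to power a larger trial.

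No section defines the intention-to-treat set, gives an expected dropout rate, says how a missing outcome survey is handled, or plans a sensitivity analysis. The two-week allowance under Study Procedure covers diaries and reading logs, not the outcome surveys.

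**The concern.** A t-test leaves out anyone without a follow-up score, and a paired t-test needs both scores. With no rule for missing surveys, the analysis defaults to participants who returned them, and that alone does not deliver an analysis of everyone randomised.

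Selective return is plausible here. The arms have different tasks (seven meditation and yoga modules with a diary, against reading with a log). Interest in IEO is an inclusion criterion, and controls are still waiting for it at day 30. Surveys are completed remotely, participants may stop at any time, and the outcomes are self-reported stress and burnout, which could affect whether a busy employee answers.

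At stake is the effect estimate. A spurious difference of 0.1 to 0.2 SD, in either direction, would feed into the sample size of the larger trial.

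**Working it through.** **Inputs.** From the documents: at least 60 participants, two groups by simple randomisation, two-sided 0.05, surveys at baseline and day 30 (and day 60 for controls). Assumed, because the documents do not say: 30 per arm, dropout rates, dropout mechanism, baseline-outcome correlation (rho). True effect is 0 throughout; results are in SD units, and negative means lower stress in the IEO arm.

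**1. The plan's own figure.** The 60 has no effect size, SD, power or dropout rate behind it, so it cannot be reproduced. For scale, 30 per arm with complete data detects (1.960 + 0.842) x sqrt(2/30) = 0.72 SD at 80% power.

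**2. When is the completer t-test biased?** Day-30 t-test, rho = 0.5, 20,000 simulated trials per row (adjusted estimate from 10,000):

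| Missing, control / IEO | Mechanism | t-test bias | Type I error | Baseline-adjusted bias |
|---|---|---|---|---|
| 0 / 0 | none | 0.00 | 5.1% | 0.00 |
| 10% / 40% | random within arm | 0.00 | 5.0% | 0.00 |
| 10% / 40% | IEO depends on baseline | -0.17 | 8.4% | 0.00 |
| 10% / 20% | IEO depends on follow-up score | -0.18 | 9.7% | -0.13 |
| 10% / 40% | IEO depends on follow-up score | -0.34 | 19.0% | -0.25 |
| about 20% / 20% | only IEO depends on follow-up score | -0.18 | 9.1% | -0.14 |
| about 21% / 21% | opposite dependence on follow-up score | -0.36 | 25.1% | -0.28 |
| about 21% / 21% | same mechanism in both arms | 0.00 | 5.0% | 0.01 or less |

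Unequal rates alone do no harm, and equal rates give no protection. What matters is whether missingness relates to outcome differently by arm.

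**3. Size when IEO dropout depends on baseline stress.** Controls complete, rho = 0.6, 8,000 trials per setting. The slope is the rise in the log odds of missing per SD of baseline stress.

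| IEO missing | Slope | Day-30 t-test bias | Type I error |
|---|---|---|---|
| 20% | 0.5 | -0.056 | 5.2% |
| 20% | 1.0 | -0.099 | 6.4% |
| 20% | 1.5 | -0.134 | 7.2% |
| 30% | 0.5 | -0.087 | 6.2% |
| 30% | 1.0 | -0.153 | 7.9% |
| 30% | 1.5 | -0.195 | 10.1% |

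Repeat runs agree within simulation error (up to -0.20). Baseline-adjusted regression on the same completers had bias within 0.005 and type I error of about 5%.

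**4. A change-score t-test goes the other way.** Let m be the amount by which mean baseline stress in IEO returners falls below that of controls. The day-30 bias is -rho x m and the change-score bias is m - rho x m = (1 - rho) x m. So the change-score bias is the day-30 bias times -(0.4/0.6):
- 20% missing: 0.056, 0.099 and 0.134 become +0.037, +0.066 and +0.089.
- 30% missing: 0.087, 0.153 and 0.195 become +0.058, +0.102 and +0.130.

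Across the simulation runs the range was +0.04 to +0.14, against IEO.

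**5. Precision.** Adjustment multiplies the standard error by about sqrt(1 - 0.6^2) = 0.80. After the small cost of estimating the slope and of baseline imbalance among returners, the simulated reduction was about 17-19%.

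**6. Limit of adjustment.** When dropout depends on the follow-up score, bias remains after adjustment: -0.13 to -0.28 in step 2, and about -0.17 SD in a run with rho = 0.6.

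**7. Within-group tests.** A paired test, and the Aim 3 comparison after cross-over, estimate mean change among people with both scores. That equals mean change in the whole group only if missingness is unrelated to change. No difference between arms is needed for this bias.

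**The case against.** The strongest reply has five parts.

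- **Silence is not contradiction.** A reader might infer that the named tests contradict intention-to-treat. They do not: a t-test can compare people by assigned arm whatever their adherence, and it could follow imputation. The surveys are already scheduled by group and day with no adherence condition. This stands. What is missing is any handling of absent scores.
- **Dropping incomplete cases is not the whole cause.** Under baseline-dependent dropout, regression on completers is already unbiased, and the plan names adjusted regression. This stands as far as it goes, but the plan makes it optional and does not name the baseline score.
- **Rates and direction.** It is tempting to read unequal dropout as bias in itself, or to say the bias favours IEO. Neither is supported. Step 2 shows no bias from unequal rates alone, and the direction in steps 3 and 4 depends on a choice the plan leaves open.
- **The SD.** A reader might also infer that the SD passed to the larger trial is distorted. In a rerun the pooled SD among completers was 0.978 to 0.992 against a true 1.0, about 2% at worst.
- **Proportion.** This is a feasibility study without a power claim, and the dropout rates are assumed. With 21 and 30 returners the standard error is sqrt(1/21 + 1/30) = 0.28 SD, larger than the biases in step 3. At 20% missing with the mildest slope, type I error is essentially nominal. That lowers the weight of the point but does not remove it: the estimate is meant to inform a larger trial, Aim 2 is tested at 0.05, and the remedy uses scores already collected.

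**Conclusion.** The point holds and should be acted on before analysis. The plan claims intention-to-treat, commits to an unadjusted t-test, and has no method for missing surveys. As written, the estimates rest on participants with a follow-up score.

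Under 20-30% IEO-arm dropout tied to baseline stress, with complete controls and a correlation of 0.6, the bias is about -0.06 to -0.20 SD for a day-30 t-test (type I error about 5-10%) or +0.04 to +0.14 SD for a change-score t-test. It is about 0 after baseline adjustment. These sizes rest wholly on assumed dropout, since the documents give none. If missingness is random within arm, or works the same way in both arms, the comparison is not biased. If it depends on the unseen follow-up score, adjustment is not a full cure, which is why a sensitivity analysis is also needed.

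**What to change.** - **Aim 2.** Make the primary analysis a baseline-adjusted model of the day-30 score by assigned arm: either ANCOVA, or a mixed model with a common baseline mean that uses every randomised participant with any score. Keep the t-test as supportive, and say whether it is on day-30 scores or on change.
- **Aim 3.** Use a mixed model on the control group's baseline, day-30 and day-60 scores, with day 60 versus day 30 as the named contrast. An arm-by-visit contrast does not fit this aim, because both arms have been offered IEO by day 60.
- **Analysis set.** Define it as all randomised participants by assigned arm, and report missing surveys by arm and time point.
- **Sensitivity.** Add one missing-not-at-random analysis by delta-adjusted or control-based multiple imputation. Single imputation would understate the variance.
- **While editing.** Both sections place the paired comparison at six weeks, but the surveys are at 30 and 60 days; reconcile these.

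The cost is a few sentences in the plan, a few lines of SAS and slightly more analysis work. Design and data collection do not change.
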